The Investigator will document all adverse signs and symptoms regardless of severity or frequency that are either volunteered by subjects or observed during the course of the study that are related to the device. The Investigator will also record adverse experiences of subjects resulting from concurrent illnesses, reactions to concurrent medications, or progression of disease states that the Investigator deems related to the device. Included in the description will be the nature of the sign or symptom, the date of onset, whether the event was serious, the severity, the relationship to study procedures or investigational device, the action taken, the date of resolution, and the outcome. The Principal Investigator will determine the relationship of the adverse device effect to the investigational device.

Unanticipated Adverse Device Effects

For device studies, part 21 CRF 812.3(s) uses the term unanticipated adverse device effect which is defined as any serious adverse effect on health or safety or any life-threatening problem or death caused by, or associated with, a device, if that effect, problem, or death was not previously identified in nature, severity, or degree of incidence in the investigational plan or application (including a supplementary plan or application), or any other unanticipated serious problem associated with a device that relates to the rights, safety, or welfare of subjects.

All unanticipated adverse effects will be graded as follows:

Mild: Sign or symptom, usually transient, non-life-threatening requiring no special treatment and generally not interfering with usual activities.

Moderate: Sign or symptom, non-life-threatening which may be ameliorated by simple therapeutic measures and may interfere with usual activity.

Severe: Sign or symptom that is intense or debilitating but non-life-threatening and that interferes with usual activities. Recovery is usually aided by therapeutic measures and the discontinuation of the study device may be required.

Serious: Any untoward medical occurrence that at any time results in death or life-threatening illness, resulting in persistent or significant disability/incapacity.

The relationship of the adverse effect to the study is defined as follows:

Probable: An adverse event has a strong temporal relationship to study device, and another etiology is unlikely or significantly less likely.

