Possible: An adverse event has a strong temporal relationship to the study device, and an alternative etiology is equally or less likely compared to the potential relationship to study device.

Probably not: An adverse event has little or no temporal relationship to the study device and/or a more likely alternative etiology exists.

Not related: An adverse event has no temporal relationship to study device or has a much more likely alternative etiology.

Reporting Adverse Events (AE) and Serious Adverse Events (SAE)

The Investigator must report all unanticipated adverse device events that are serious in nature to the clinical study monitor immediately or within twenty-four hours by telephone (see below). If such an unanticipated adverse device event is reported after normal working hours, the

 Candela Corporation Confidential	Clinical Study of the CO₂RE Laser Device for Treatment of Vulvar Lichen Sclerosus				
	Protocol #	DHF25211	Rev. Date	February 19, 2019	Page 19 of 39

Investigator will leave a voice message at the monitor's telephone number with accompanying report of the unanticipated adverse device event sent to the e-mail address below:

[name], Global VP of Clinical and Regulatory Affairs

Candela Corporation

Telephone Number (mobile): [contact]

Email: [contact]

A written report prepared by the Principal Investigator must follow within five working days to both the IRB and to Candela Corporation and should include a full description of the event and sequence.

Research records will be available to study personnel, the sponsor, Ethics Review Committee/Institutional Review Board (IRB) and regulatory agencies as required. Research records may be used for purposes of medical education, after removal of subject names or other identifying information. In the Informed Consent, the subjects will be informed that the photographs and video taken of them during the study may be made available to the sponsor for marketing and instructional purposes, after removal of identifying information. All images collected will be stored without personal subject identifiers at the site and at Syneron Candela.

Device Failures and Malfunctions

Definitions of Device Failure

Device Failure: A device has failed if it is used according to the Sponsor's instructions but has failed to perform as expected.

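### The adverse-effect scale makes Serious a fourth severity grade, and its wording leaves some life-threatening events ungraded and puts disabling, non-life-threatening events under Severe

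*Protocol*

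**What the plan says.** Under Adverse Events, the Anticipated Adverse Effects section lists what the investigator must describe for each event. The list includes "whether the event was serious, the severity, the relationship to study procedures or investigational device", so seriousness and severity are separate items.

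The next section, Unanticipated Adverse Device Effects, first gives the regulatory definition, which covers "any serious adverse effect on health or safety or any life-threatening problem or death caused by, or associated with, a device", provided the effect was not previously identified. It then introduces a scale: "All unanticipated adverse effects will be graded as follows". There are four levels. The lowest two, Mild and Moderate, are both restricted to events that pose no threat to life, and differ in the need for treatment and the disturbance of daily life. The third, Severe, carries the same restriction: "Sign or symptom that is intense or debilitating but non-life-threatening and that interferes with usual activities". The fourth and highest level, Serious, is defined as "Any untoward medical occurrence that at any time results in death or life-threatening illness, resulting in persistent or significant disability/incapacity".

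The section Reporting Adverse Events (AE) and Serious Adverse Events (SAE) requires the investigator to "report all unanticipated adverse device events that are serious in nature" to the study monitor at once or within 24 hours. A written report to the IRB and the sponsor follows within five working days. The protocol defines serious nowhere else and gives no other scale for the severity of adverse events. Severity of adverse events is part of a safety endpoint (Secondary Safety Endpoints, item 3).

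**The concern.** Severity describes how intense an event is. Seriousness describes its outcome or the danger it poses, and it decides how fast the event is reported. The protocol asks for both and then supplies one scale on which Serious is simply the step above Severe. An event graded Serious therefore carries no intensity grade, and an event graded Severe is by construction not Serious.

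The Serious sentence adds a second problem. Its disability clause follows a comma with no 'or', so it reads as a further condition on what comes before it and not as a criterion of its own. That is narrower than the regulatory definition a few lines above.

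Two things are at stake. Investigators at up to four sites could classify the same event differently. And an investigator who turns to the only available definition of serious to decide on a 24-hour call could conclude that a disabling event does not qualify.

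**Working it through.** No arithmetic applies. The check takes five kinds of unanticipated event through the four grade definitions, first with the Serious sentence as written and then with an 'or' supplied before the disability clause.

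| Event | Mild, Moderate or Severe? | Serious, as written? | Serious, with 'or'? |
|---|---|---|---|
| (a) Life-threatening, with persistent disability | No, all exclude threat to life | Yes | Yes |
| (b) Life-threatening, with significant but temporary incapacity, then full recovery | No | Yes, because significant is an alternative to persistent | Yes |
| (c) Life-threatening, with neither persistent nor significant disability | No | No: **no grade applies** | Yes |
| (d) Persistent or significant disability, no threat to life | Severe | No: **graded Severe** | Yes, but it still meets Severe as well |
| (e) Death | No | Only if death also had to cause disability, which is absurd | Yes |

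**Row (e)** shows that the sentence is defective and suggests a dropped 'or'. One could instead attach the disability clause to life-threatening illness only, leaving death to stand alone. That rescues (e), but (c) remains ungraded and (d) remains Severe.

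**Row (c) against the device-effect definition.** That definition names death and any life-threatening problem in their own right. Event (c) is therefore covered by the definition if device-associated and not previously identified, yet has no place on the scale in the same section.

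**Row (d) against the device-effect definition.** Disability is not named there. Event (d) can enter only as a serious effect or serious problem, and the only text saying what serious means is the defective sentence. An example is disabling vulvar scarring from the laser. Scarring is not among the anticipated treatment effects (pain, swelling, bruising, blistering, burn, infection). It is named as a procedural risk only under Vulvar Biopsy Procedure.

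**Seriousness against severity.** Supplying the 'or' closes the gap in (c) but does not separate the two concepts. Events (a), (b), (c) and (e) are then Serious with no severity grade, and (d) satisfies two levels of one scale. The mismatch with the separate recording of seriousness and severity does not depend on how the sentence is repaired.

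**The case against.** The strongest reply is that this is a slip of one word, which any investigator would repair. The literal reading is absurd for death, and with an 'or' supplied every event in the table is Serious. The reporting rule is worded by the nature of the event and does not cite the scale. The device-effect definition already covers any life-threatening problem or death, and the study commits itself to 21 CFR 812 and to GCP (Ethics and Good Clinical Practice).

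Much of this stands, and it limits the point. A reader might infer more than the protocol supports in four ways:

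- *That Serious requires lasting disability, so that no life-threatening event with full recovery can be graded.* The clause accepts significant disability as an alternative to persistent disability, so event (b) is Serious even as written. Only event (c) is ungraded.
- *That life-threatening events will miss the 24-hour report.* The rule does not use the grade, and the device-effect definition points toward reporting. A missed report is possible only if the investigator reads the rule through the grade.
- *That the problem affects all adverse events, or leaves form fields that cannot be completed.* The scale is introduced for unanticipated effects only, and the adverse-event form is not shown. A four-level scale can still be tabulated; what is lost is the separate severity of events graded Serious.
- *That an anesthetic reaction illustrates the gap.* Allergic reaction to anesthetic is a listed biopsy risk, and such a reaction would also have to be associated with the device. It is a weak example.

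The 'or' might have been lost when the PDF was read, but nothing in the text shows this.

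The reply does not dispose of the rest. It leaves seriousness and severity merged, and it leaves event (d) dependent on the defective sentence. It also asks investigators at several sites to make the same unstated correction.

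**Conclusion.** The point holds as a wording defect in a safety definition. Serious is placed on a severity scale although the protocol has seriousness and severity recorded separately, and this is so on any reading of the sentence. On the literal reading, two kinds of unanticipated event are misplaced. A life-threatening event without persistent or significant disability has no grade. A disabling event without threat to life is graded Severe. The first conflicts directly with the device-effect definition in the same section.

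The effect on expedited reporting is a risk and not a certainty. It is greatest for disabling, non-life-threatening events, because the device-effect definition does not name them. It rests on the assumption that an investigator would look to the only stated definition of serious when applying the reporting rule. The protocol gives no event rates, so the number of events affected among up to 45 subjects cannot be estimated. The defect should be corrected because it bears on expedited safety reporting and costs little to repair.

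**What to change.** 1. Keep Mild, Moderate and Severe as the severity scale. Remove the exclusion of life-threatening events from Severe, so that every event can receive a severity grade.
2. Take Serious off that scale. Record it as a separate yes/no with independent criteria joined by 'or': death; life-threatening; persistent or significant disability or incapacity. Check the list against the device-effect definition and the GCP guideline that the protocol cites, and add any criterion the sponsor finds missing.
3. In the reporting section, refer the 24-hour rule explicitly to that yes/no.

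The cost is the rewording of one paragraph, a cross-reference in the reporting section and, if the adverse-event form carries the present four-level scale, a change to one field. The downside is possibly a few more expedited reports. No efficacy analysis is affected.

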APPENDIX I – SUBJECT SYMPTOMS SEVERITY SCALE*

At baseline and at the four follow-up visits, the study subject will complete assessments for severity of the following symptoms associated with their vulvar lichen sclerosus.

Subject Symptoms

Symptom	Presence of symptoms	Severity
Itch	Yes / No	1, absent/never 2, sometimes/occasionally 3, often 4, most of the time 5, all the time
Pain unrelated to intercourse (burning, soreness, discomfort, etc.)	Yes / No	1, absent/never 2, sometimes/occasionally 3, often 4, most of the time 5, all the time
Superficial (introital) dyspareunia (pain occurring at the moment of penetration)	Yes / No	1, absent/never 2, sometimes/occasionally 3, often 4, most of the time 5, all the time

Skin tearing or external bleeding with intercourse	Yes / No	1, absent/never 2, sometimes/occasionally 3, often 4, most of the time 5, all the time
Quality of life	Yes / No	1, no impact 2, barely affected 3, slightly affected 4, moderately affected 5, strongly affected
Decrease in sexual function – desire to have sexual intercourse is decreased due to physical appearance or self-esteem	Yes / No	1, no impact 2, barely affected 3, slightly affected 4, moderately affected 5, strongly affected

*Based on: Sheinis M, Selk A. Development of the Adult Vulvar Lichen Sclerosus Severity Scale-A Delphi Consensus Exercise for Item Generation. J Low Genit Tract Dis. 2018 Jan;22(1):66-73. doi: 10.1097/LGT.0000000000000361.

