Table 2. Study Measurements

Assessment	When to conduct	Method
Complete the Inform Consent form and Eligibility Screening and Medical History	During the screening visit / prior to the 1 st treatment	Physician or staff will complete the form with the study subject
PAP smear if not up-to-date (within 3 years according to ACOG guidelines)		Patient should provide lab results of up-to-date normal cell cytology
Urine pregnancy test for women capable of becoming pregnant		Patient should have a negative pregnancy test
Gynecological exam		Physician will examine the vulvar and vaginal area for any signs of active infection or atypical nevi
Vulvar biopsy of treatment area (optional)	Prior to the 1 st treatment and at the 6-week and 6-month follow-ups	Biopsies will be obtained from up to 10 subjects to conduct histological assessment. Lab reports will be provided to show changes in markers compared to baseline.
Subject assessment of symptoms	
 • Baseline or pre-Tx. 1 • At the 6-week, 3-month, 6-month and 12-month follow-up visits 	Subjects will complete the Symptom Severity Questionnaire, according to the pre-defined scales (Appendix I)
Physician assessment	
 • Baseline or pre-Tx. 1 • Prior to treatments • At the 6-week, 3-month, 6-month and 12-month follow-up visits 	Physician will assess clinical signs associated with VLS, according to the pre-defined scales (Appendix II)
Subject assessment of sexual function	
 • Baseline or pre-Tx. 1 • At the 3-month and 6-month follow-up visits 	Subjects will complete the Female Sexual Function Index (FSFI) – Appendix III
Clinical evaluation and photographs of treated area	
 • Baseline or pre-Tx. 1 • Prior to treatments • At the 6-week, 3-month, 6-month and 12-month follow-up visits 	Physician will evaluate the treatment area. Physician or staff will take photographs of the treatment area (Appendix IV)
Treatment pain assessment	Immediately after each treatment	NSR Scale (Appendix V)
Subject 1-week daily diary - reviewed at the 1wk FU after the first treatment	The daily diary will be provided at the 1 st treatment visit and reviewed by phone during the 1-week safety evaluation	Subjects will be requested to complete a daily diary with data regarding their comfort, AE, and activity (7 days of follow-up post 1st treatment) – Appendix VI

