The Study Personnel will obtain written Informed Consent prior to the subject's participation in any study procedures. The Study Personnel will inform the subjects of the experimental procedure to be utilized and assure the subjects that their decision regarding participation in the study will have no bearing on the quality of medical care received and that their decision whether to participate in the study is strictly voluntary.

During the initial interview, the subject will be assured that they are free to change their mind and will be allowed to participate in the study or withdraw from the study with no adverse effect on their standard medical care.

Monitoring Plan

At least 3 monitoring visits are projected during the whole study. The frequency of which will be based on enrollment, study activities and the study visit scheduled. The first visit is scheduled at the initiation of the study prior to the first subject treatment in the study. The second visit is scheduled after enrollment and treatment has been initiated and a third visit will be for a close-out visit for the study. Interim visits may be conducted as needed to assure compliance to the study protocol and regulatory requirements. The number and frequency of monitoring visits may also be increased per the sponsor decision to collect data and images post treatment.

Case Report Forms

Paper case report forms will be used in this trial. All protocol-required information collected during the study must be entered in the appropriate field of the case report form (CRF). The investigator, or designated representative, should complete the appropriate CRF fields as soon as possible after information is collected. The information must match the information that exists as source documents in the clinic chart, hospital chart, and/or investigator's files. An explanation should be given for all missing data.

It is the investigator's responsibility to assure the accurate completion, review, and approval of all CRFs and the timely completion and submission of all adverse event forms.

Record Maintenance

The investigator shall retain a copy of all study documents in accordance with FDA regulations which specify that records should be kept for a period of two years: 1) following the date a marketing application either is approved or disapproved for use, or 2) following notification to the FDA that no application is being filed and/or that the study has been discontinued.

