APPENDIX III – FEMALE SEXUAL FUNCTION INDEX*
Female Sexual Function Index (FSFI) ®

Subject Identifier _____ Date _____

INSTRUCTIONS: These questions ask about your sexual feelings and responses during the past 4 weeks. Please answer the following questions as honestly and clearly as possible. Your responses will be kept completely confidential. In answering these questions the following definitions apply:

Sexual activity can include caressing, foreplay, masturbation and vaginal intercourse.

Sexual intercourse is defined as penile penetration (entry) of the vagina.

Sexual stimulation includes situations like foreplay with a partner, self-stimulation (masturbation), or sexual fantasy.

CHECK ONLY ONE BOX PER QUESTION.

Sexual desire or interest is a feeling that includes wanting to have a sexual experience, feeling receptive to a partner's sexual initiation, and thinking or fantasizing about having sex.

1. Over the past 4 weeks, how often did you feel sexual desire or interest?

- Almost always or always
- Most times (more than half the time)
- Sometimes (about half the time)
- A few times (less than half the time)
- Almost never or never

2. Over the past 4 weeks, how would you rate your level (degree) of sexual desire or interest?

- Very high
- High
- Moderate
- Low
- Very low or none at all

Sexual arousal is a feeling that includes both physical and mental aspects of sexual excitement. It may include feelings of warmth or tingling in the genitals, lubrication (wetness), or muscle contractions.

3. Over the past 4 weeks, how often did you feel sexually aroused ("turned on") during sexual activity or intercourse?

No sexual activity
 Almost always or always
 Most times (more than half the time)
 Sometimes (about half the time)
 A few times (less than half the time)
 Almost never or never

4. Over the past 4 weeks, how would you rate your level of sexual arousal ("turn on") during sexual activity or intercourse?

No sexual activity
 Very high
 High
 Moderate
 Low
 Very low or none at all

5. Over the past 4 weeks, how confident were you about becoming sexually aroused during sexual activity or intercourse?

No sexual activity
 Very high confidence
 High confidence
 Moderate confidence
 Low confidence
 Very low or no confidence

6. Over the past 4 weeks, how often have you been satisfied with your arousal (excitement) during sexual activity or intercourse?

No sexual activity
 Almost always or always
 Most times (more than half the time)

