- About equally satisfied and dissatisfied
- Moderately dissatisfied
- Very dissatisfied

16. Over the past 4 weeks, how satisfied have you been with your overall sexual life?

- Very satisfied
- Moderately satisfied
- About equally satisfied and dissatisfied
- Moderately dissatisfied
- Very dissatisfied

17. Over the past 4 weeks, how often did you experience discomfort or pain during vaginal penetration?

- Did not attempt intercourse
- Almost always or always
- Most times (more than half the time)
- Sometimes (about half the time)
- A few times (less than half the time)
- Almost never or never

18. Over the past 4 weeks, how often did you experience discomfort or pain following vaginal penetration?

- Did not attempt intercourse
- Almost always or always
- Most times (more than half the time)
- Sometimes (about half the time)
- A few times (less than half the time)
- Almost never or never

19. Over the past 4 weeks, how would you rate your level (degree) of discomfort or pain during or following vaginal penetration?

- Did not attempt intercourse
- Very high
- High
- Moderate
- Low
- Very low or none at all

Thank you for completing this questionnaire

Copyright ©2000 All Rights Reserved

Page 5 (of 5)

[figure not shown]

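### Two of the six Appendix I symptom items depend on intercourse but have no answer for women who did not attempt it, so at 6 weeks and 12 months avoidance can read as resolution.

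*Protocol*

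**What the plan says.** The primary endpoint (Protocol, Primary Endpoint) is the change from baseline in symptoms, clinical signs and architectural changes at 6 weeks, 3, 6 and 12 months. Symptoms are self-rated with the six items of Appendix I. Two of these are "Superficial (introital) dyspareunia (pain occurring at the moment of penetration") and "Skin tearing or external bleeding with intercourse". For each, the woman states whether the symptom is present (Yes/No) and rates it "1, absent/never 2, sometimes/occasionally 3, often 4, most of the time 5, all the time". Appendix I gives no recall period and no answer for intercourse that was not attempted.

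The FSFI (Appendix III) has both features. Its instructions say "These questions ask about your sexual feelings and responses during the past 4 weeks", and items 17 to 19 each offer "Did not attempt intercourse".

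The schedules differ. Table 2 places the symptom assessment at baseline and "At the 6-week, 3-month, 6-month and 12-month follow-up visits", but the FSFI at baseline and "At the 3-month and 6-month follow-up visits" only. The assessments listed under Follow-up Visits include no question on sexual activity. The nearest general safeguard is in Case Report Forms: "An explanation should be given for all missing data".

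**The concern.** A woman who is not having intercourse, whether from pain, lack of a partner or choice, can truthfully answer No and never on both items. So can a woman whose symptom has gone. Entry does not require sexual activity: inclusion criterion 7 asks for one or more of several symptoms, and itch alone is enough.

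If the answers are taken at face value, women who stop read as improved, women who resume with some pain read as worse, and women inactive throughout dilute the change. The net bias can therefore run either way, and there is no control group in which the artefact would show.

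Linking the baseline FSFI would take out women inactive at baseline at every visit. What remains at 6 weeks and 12 months is the woman active at baseline who later answers never. In that group, stopping can read only as improvement or no change. An analysis rule written later cannot repair this, because the information was not collected.

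**Working it through.** The Protocol states no figure on this point to reproduce.

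**Scope (Appendices I and II).** There are 6 symptoms + 12 signs + 6 architectural changes = 24 items. Two of the 24, or two of the six symptoms, depend on intercourse. Appendix I is used at four follow-up visits and the FSFI at two of them, which leaves 6 weeks and 12 months uncovered.

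**Can a neighbouring FSFI fill the gap?**
- The 3-month visit is at about week 13, ± 2 weeks = weeks 11 to 15. Four weeks of recall reach back to week 13 − 4 = 9 (range 7 to 11).
- The 6-week visit falls at weeks 6 ± 2 = 4 to 8. The 3-month FSFI reaches that range only when its own visit is early.
- The 12-month visit is 12 − 6 = 6 months, about 26 weeks, after the last FSFI.

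**Can other entries fill it?** The Yes/No column is equally ambiguous. The sixth symptom item asks about desire reduced by appearance or self-esteem, not about whether intercourse took place. The missing-data rule applies only to blanks, and a recorded never is not blank.

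**Illustration of size, one item.** Only the 45 comes from the Protocol; all rates are assumed. Let *a* = share active at baseline (0.6; range 0.8 to 0.4), *s* = share of active women who stop, *r* = share of inactive women who resume, and *p* = share of non-attempters who answer 1 (the rest leave a blank and drop out of the change). The score when active is 4, so a stopper who answers 1 changes by −3.

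1. *All women, no true effect, s = 0.2, r = 0.* Change = −3sap / [(1−s)a + sap + (1−a)p].
   - With a = 0.6 and p = 1: −0.36 / (0.48 + 0.12 + 0.40) = −0.36.
   - With a = 0.6 and p = 0.5: −0.18 / (0.48 + 0.06 + 0.20) = −0.24. With p = 0: 0.
   - For a = 0.8: −0.48, −0.29, 0. For a = 0.4: −0.24, −0.18, 0.
   - At p = 1 the false change cancels if inactive women resume at score 4 with r = sa/(1−a): 0.12/0.40 = 30% (80% at a = 0.8; 13% at a = 0.4).

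2. *All women, true fall of 2.0 in active women, nobody stops, half of the inactive resume at score 2.* Change = [−2a + 0.5(1−a)p] / [a + (1−a)p].
   - With a = 0.6 and p = 1: (−1.2 + 0.2)/1 = −1.0. With p = 0.5: −1.1/0.8 = −1.375. With p = 0: −2.0.

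3. *Only women active at baseline (from the baseline FSFI), no true effect.* Change = −3sp / [(1−s) + sp].
   - s = 0.1: −0.30 (p = 1), −0.15/0.95 = −0.16 (p = 0.5), 0 (p = 0).
   - s = 0.2: −0.60, −0.30/0.90 = −0.33, 0.

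Cases 1 and 2 describe answers taken at face value. Case 3 is what remains at 6 weeks and 12 months after the baseline FSFI has been used.

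**The case against.** The strongest reply concerns reach, not fact. Case 2 and the cancellation rates in case 1 are driven by women inactive at baseline, whom the baseline FSFI can identify. Once they are removed, case 2 returns exactly −2.0. That is right: the lasting loss is the single pathway in case 3.

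Second, without a recall period a woman avoiding intercourse because of pain may rate her last or usual experience, which records no false improvement. That also stands. The figures with every non-attempter answering never are the upper end, and the range starts at zero.

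Third, every rate is assumed, and the Protocol sets no composite score or success criterion through which two items would contaminate the other 22. This limits the importance but does not remove the ambiguity in the two items.

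Fourth, the printed questionnaire and CRF are not shown and might carry a further box or instruction. That cannot be excluded, but the Protocol makes Appendix I the pre-defined scale, and Appendix I defines none.

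Finally, FSFI items 17 to 19 concern intercourse, which the FSFI defines as penile penetration, while the dyspareunia item speaks of penetration; and the FSFI is a copyrighted 19-item instrument. Both points count in favour of the tick-box over borrowing the FSFI items.

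**Conclusion.** The point holds and should be fixed; its importance is minor to moderate. Following Appendix I and the schedule as written, a woman active at baseline who has stopped intercourse and one whose symptom has resolved can give identical primary-endpoint answers at 6 weeks and 12 months, and nothing else scheduled tells them apart. At 3 and 6 months the FSFI can do so by cross-linking.

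The size is not known. Under the case 3 assumptions (score 4 when active, 10% to 20% stopping, no true effect) the false improvement per item lies between 0 and 0.60 points, depending on how non-attempters answer. The other four symptom items and all of Appendix II are unaffected.

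**What to change.** Add a box for no intercourse attempted, with a stated recall period (for example 4 weeks, to match the FSFI), to the two items at every symptom assessment. Alternatively, collect FSFI items 17 to 19 at 6 weeks and 12 months as well. Do not score that answer as No or as 1. Report the severity change in women active at both visits together with the shifts between active and not active, because the first alone conditions on behaviour after treatment. The data field belongs in the Protocol and CRF; the scoring and reporting rule may sit in the SAP.

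If forms are already in use, identify non-attempters from FSFI items 17 to 19 at baseline, 3 and 6 months, and state the limitation at 6 weeks and 12 months.

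The cost is one box and one recall line on a paper form, or three existing items at two more visits. The price is fewer women in the severity change for these two items: at most 45 × 0.6 = 27 (36 at 80% active, 18 at 40%), and about 27 × 0.8 = 22 (29, 14) if 20% of them stop.
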